2.1 Source(s) of Support

Type/Source	Grant Title	Name of PI on Grant	Status
Federal Agency NIH, National Institutes of Health	Ischemic conditioning as a neurorecovery agent post stroke	[name]	AWARDED
Attachment Name	Category	Version	Date Attached
SubmittedApp_20150122.pdf	Grant from funding source or private foundation/association	1	06/20/16

3. Research Team

4.6 Will the study involve any of the following activity at WUSM or any BJC hospitals, even if subjects or their insurance will not be billed for the item or service, and regardless of the study funding source (including studies with departmental or no funding)?

- Procedures, tests, examinations, hospitalizations, use of Pathology services, use of clinic facilities or clinical equipment, or any patient care services, including services conducted in the Clinical Research Unit; or
- Physician services or services provided by non-physicians who are credentialed to bill (ARNPs, Physician Assistants, etc.)

Yes

4.7 Does this project involve administration of recombinant DNA (gene therapy) or microorganisms?
No

4.8 Does this study involve the use of human embryonic stem cells or human induced pluripotent stem cells?
No

4.9 Does this study involve research in which a human embryo or embryos are destroyed, discarded, or knowingly subjected to risk of injury or death greater than that allowed for research on fetuses in utero?

No

4.10 Will a Certificate of confidentiality be used for this research?
No

4.11 Does this project need to be registered on ClinicalTrials.gov?
No

4.12 Title that should appear in Epic (and will be visible in the patient medical record):
N/A-study does not need to go into Epic

4.13 Select one person from the study team that should appear in Epic as the contact person for this study:
[name]

4.14 Do you want to request that an ordering tool be built for your study in Epic?
No

4.15 Would you like to submit a request for the Epic team to consider your study for the use of BPA (Best Practice Advisory) in Epic?
No

4.16 Would you like to submit a request for the Epic team to build your questionnaires in Epic for the purposes of recruitment?
No

4.17 Will any external monitors require access to this study in Epic?
No

4.19 Mark all that apply to your study:

1. Protocol

1.1 Is there a separate, written protocol that will be submitted in addition to this form? (Note: a grant application is not considered to be a protocol)

Yes

Attachment Name	Category	Version	Date Attached
RLIC_protocol.docx	Intervention: Separate Written Protocol	9	10/15/15

1.1.a Who initiated/provided the protocol?
WUSTL Investigator

1.1.b Protocol#:

1.1.c Protocol Version#:
8

1.1.d Protocol Date
09/28/2015

1.1.e Provide a list of the amendments for this study (this may be left blank if none). Any amendments previously listed should not be removed.

1.2 Select up to three key words below that best describe this research study:

- Neurology
- Physical Therapy

1.3 Provide a short summary/abstract of the purpose and procedures of the study proposed in this IRB application.

- DO NOT include information on studies not proposed in this application.
- Use LAY terminology only. This must be easily understandable by IRB community members and nonscientists.
- DO NOT cut and paste technical abstracts from source of support applications that may not be understood by a general audience.

The purpose of this study is to determine if remote limb ischemic conditioning (RLIC) can serve as an agent to enhance motor performance and learning in humans. Our immediate goal is to test if remote limb ischemic conditioning paired with training results in greater improvements in performance and learning compared to sham conditioning paired with training in neurologically-intact adults. Our long-term goal is to determine if remote limb ischemic conditioning can improve rehabilitation outcomes for people with stroke.

RLIC will be achieved by wearing blood pressure cuff which is alternately inflated and deflated. This study will have two randomly assigned groups and will use a repeated measures design. Group one will consist of neurologically intact subjects who receive RLIC treatment to 20mmHg above their systolic BP and group two will consist of neurologically intact subjects who receive a sham treatment. Study procedures include: RLIC treatment, questionnaires, balance training, and arm motor training. The study consists of 7 visits plus two follow up appointments and will last up to 6 weeks. Visits will last from 0.5-2.5 hours, depending on the visit.

1.8 Check all materials/methods that will be used in recruiting participants:

Study staff will distribute approved flyers to various locations in the St. Louis area (e.g., Barnes Jewish Hospital, Washington University, local cafes etc.); these materials will include information about study procedures, time commitment, compensation, and how to contact [name] research laboratory. Study team members will get permission at each site before leaving flyers. If a participant calls in response to an advertisement, a research team member will answer any questions related to the study, will ask 8 screening questions (no PHI), offer to send potential participants a copy of the consent form, and will encourage them to call if they have questions.

Consent Process:

A member of the research team will meet with the potential participant individually at the beginning of the first visit to go over the consent document. The research team member will place a copy of the consent in front of the potential participant and will review each section of the document. The research team member will then give the potential participant time to read the document and encourage the individual to ask questions. If the individual does not wish to sign the consent, the research team member will thank the individual for his or her time and the meeting will conclude. If the individual needs more time to think about participating, he or she may take the consent form home and schedule a second visit if he or she decides to participate. If the individual signs the informed consent, the research team member will make a copy of the consent and give it to the individual before the conclusion of the first visit. If the potential participant displays any signs of impairment, suggesting that he or she is not capable of providing consent, the research team member will stop the consent process, as this person would not be eligible for this study. Individuals who express that they are not interested in participating will not be contacted further.

1.14 Will participants be randomized?

Yes

1.15 Will any of the following be used to collect information from the participant or others?

- Screening questions or screening/eligibility questionnaires
- Surveys
- Questionnaires
- Stimuli
- Any other written assessments

Yes

Attachment Name	Category	Version	Date Attached
RLIC Demographic Data Collection Form.docx	Subject Data Collection Instruments	2	01/09/15
PIC Side Effects Questionnaire.docx	Subject Data Collection Instruments	1	03/04/14
Borg Exertion Scale.pdf	Subject Data Collection Instruments	2	03/11/14
RLIC Treatment Guess Form.docx	Subject Data Collection Instruments	6	10/15/15

1.16 Does this project involve creating any audio, video, or photographs?

No

1.17 Does the study include any form of deception (e.g., providing participants with false information, misleading information, or withholding information about certain study procedures)?

Examples:

- Procedure includes a cover story that provides a plausible but inaccurate account of the purposes of the research.
- Participants will be provided with false information regarding the particular behaviors of interest in the research.
- Procedures include a confederate pretending to be another participant in the study.
- Participants will be told that the research includes completion of a particular task, when in fact, that task will not be administered.
- Study is designed to introduce a new procedure (or task) that participants are not initially told about.

No

1.18 Indicate any payments or reimbursements to participants (check all that apply)

- Cash
- Check

1.19 Does this study have a plan to have an individual or committee review combined data from all participants on a periodic basis (such as summary or aggregate safety and/or efficacy data)?

Yes, but it's not described in an attached protocol

The study investigators and study staff will meet weekly to review accrued data, data confidentiality, adherence to protocol design, recruitment, and subject complaints. In addition, this study is one aim of an entire grant, and the grant has a Data Safety Monitoring Committee to meet the NIH requirements. The Data Safety Monitoring Committee does review this study as well as the other studies (separate IRB Protocols)

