Number of Subjects & Power Analysis	
Based off of our pilot data on the balance training task we need the following total sample sizes moving forward (see Table 1 below) to achieve at least 80% power to detect the mean differences of change scores (posttest – pretest) between the two treatment groups (RLIC vs. sham) based on a two-sample t-test at a significance level of 0.05. The standard deviations for change scores are assumed to be 2.5 seconds and 1.9 seconds for the RLIC and sham groups, respectively. Moving forward, we will recruit 10 subjects per group (n=40). This will give us the ability to detect differences on the balance task of at least 3 seconds or more. Differences less than 3 seconds (and smaller effect sizes) are unlikely to be clinically-relevant in future target populations. We continue to request permission to enroll 130 subjects total 51 of whom have already been enrolled) to allow for screen failures and participants who do not complete all study visits.
 
Table 1. Power analysis
 
  
 Mean difference of change score	Total sample size (assume equal sample size in each group)	
   
 7 seconds	12 (with actual power 93%)	
 
 6	12 (with actual power 85%)	
 
 5	15	
 
 4	21	
 
 3	30	
 
 2	63	
 
 1	237	
  
	Mean difference of change score	Total sample size (assume equal sample size in each group)	7 seconds	12 (with actual power 93%)	6	12 (with actual power 85%)	5	15	4	21	3	30	2	63	1	237
Mean difference of change score	Total sample size (assume equal sample size in each group)																
7 seconds	12 (with actual power 93%)																
6	12 (with actual power 85%)																
5	15																
4	21																
3	30																
2	63																
1	237																

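### The recruitment target reads as either 20 or 40, and nothing in writing keeps by-arm outcomes out of the weekly staff data review, so the 5% error rate is left unprotected

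*Combined protocol and SAP*

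**What the plan says.** **Size.** The protocol section Number of Subjects & Power Analysis sizes the trial "to achieve at least 80% power to detect the mean differences of change scores" between RLIC and sham, "based on a two-sample t-test at a significance level of 0.05". It then says "Moving forward, we will recruit 10 subjects per group (n=40" and ties this to a difference of 3 seconds. The Groups section describes two groups. Permission is also kept for 130 enrolled in total, 51 of them already enrolled. The stated reason is to cover screen failures and people who miss visits. Item 2.1.a of the IRB form gives 143.

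**Data review.** Item 1.19 of the IRB form asks about a plan to "review combined data from all participants on a periodic basis (such as summary or aggregate safety and/or efficacy data". The box ticked is "Yes, but it's not described in an attached protocol". The explanation begins "The study investigators and study staff will meet weekly to review accrued data"; the same sentence adds confidentiality, adherence, recruitment and complaints to the agenda. It goes on to say that "the grant has a Data Safety Monitoring Committee to meet the NIH requirements" and that this committee reviews the present study too.

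**Blinding and analysis.** Conditioning Parameters states blinding for participants only. Groups conceals allocation from those who judge eligibility, which protects enrolment but does not blind later testing. Data Analysis plans a mixed model and mentions no interim analysis, stopping rule or adjustment of the significance level.

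**The concern.** A single test at 0.05 has a 5% error rate only if the number at which it is made does not depend on the results so far. Two safeguards normally secure this: one stated sample size, and no comparative results for the people who run the trial until that size is reached. Here the stated size has two values. The people running the trial review accruing data every week, and no sentence excludes a comparison by arm.

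If someone did compare the arms at 20 and continued to 40 only when the result was not significant, either total could later be defended from the protocol's own sentence. The reported p-value would then understate the chance of a false positive. Separately, staff who see results by group while still testing participants could affect later performance, for example through encouragement.

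**Working it through.** **Inputs from the protocol** (Number of Subjects & Power Analysis): SDs of the change score 2.5 s (RLIC) and 1.9 s (sham); difference 3 s; significance level 0.05; power at least 80%; equal groups. Sidedness is not stated, so two-sided is assumed.

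**Step 1: which size do the plan's figures support?** With n per group,

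SE = √(2.5²/n + 1.9²/n) = √(9.86/n), and the noncentrality is 3/SE.

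| n per group | Total | SE (s) | 3/SE | Welch df | Power for 3 s |
|---|---|---|---|---|---|
| 10 | 20 | 0.993 | 3.02 | 16.8 | 81% |
| 20 | 40 | 0.702 | 4.27 | 35.5 | 98.6% |

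Ten per group is the smallest number that reaches 80% for 3 s, so that half of the sentence agrees with the stated aim. Forty in total corresponds to 20 per group. Table 1 lists a total of 30 for 3 s. This is not reproduced for two groups, where the total is 2 × 10 = 20. It equals 3 × 10, and the rows from 6 s to 1 s also equal three times the Welch per-group number. The table therefore looks like totals for three groups, but the documents do not say so. It does not settle the choice between 20 and 40.

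**Step 2: what would follow if both readings were used as test points?** The assumptions, none of which is in the documents, are no true effect, a Welch t-test at 0.05 with 10 per group, and a second test with 20 per group if the first is not significant.

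- Large-sample check: the two test statistics have correlation √(20/40) = 0.707. The chance that at least one exceeds 1.96 in absolute value is 1 − P(|Z₁| < 1.96 and |Z₂| < 1.96) = 8.3%. For one direction it is 4.2%.
- Simulation with the protocol's SDs (60,000 null trials per row):

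| Tests made at 0.05 | Any false positive | False positive favouring RLIC |
|---|---|---|
| Once, at 40 in total | 5.05% | 2.5% |
| At 20 and at 40 in total | 8.2% | 4.1% |
| After every pair from 20 to 40 in total | 13.1% | 6.6% |

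The second row uses only the two readings of the stated target. The third shows the sensitivity to more frequent looks. Its timing is purely an assumption, since the form schedules meetings, not tests.

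**Step 3: what if the looks are harmless?** If the weekly data are pooled over groups or limited to safety, or if no look affects when recruitment ends, only one test counts and the rate is 5%.

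**The case against.** The strongest reply is that the documents describe routine oversight. Accrued data is one of five agenda items, beside confidentiality, adherence, recruitment and complaints. The form's question speaks of combined and aggregate data, which suggests pooled review. No interim comparison is planned, and the sample size rests on one t-test. On this view the target is simply a slip in the text, and a slip is not a stopping rule.

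Much of this stands. A reader might infer that staff compare the arms each week and can end recruitment on a favourable result. No sentence says so. A reader might also treat the 79 places left under the ceiling (130 − 51) as an open-ended sample and quote much larger error rates. That is not supported either, because the protocol explains the ceiling as an allowance for screen failures and non-completers. It is an enrolment limit, not an analysis sample.

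Two further limits apply. Item 1.19 does not say which staff attend, so it cannot be asserted that those who train and test participants are present. The planned analysis is a mixed model, whereas the simulated test is the t-test used for sizing. The inflation comes from repeated testing of accumulating data, so a similar pattern is expected under the mixed model, but the percentages belong to the t-test.

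The reply does not remove two facts. The target has two values. And although the form's question expressly covers efficacy data, the answer does not exclude them or say that the arms are kept pooled.

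**Conclusion.** The contradiction in the target is definite: two groups of 10 make 20, not 40. The threat to the error rate is conditional. The documents leave it open but do not show that it occurs. If the arms were tested at 0.05 at both 20 and 40 in total, the two-sided false-positive rate would be about 8% instead of 5%, and about 4% instead of 2.5% for a false result in favour of RLIC. These figures rest on the protocol's SDs, normally distributed change scores, equal groups, two-sided testing and stopping at the first significant result. The point is worth acting on because a number that the trial relies on must be corrected anyway, and the protection costs almost nothing.

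**What to change.** 1. In Number of Subjects & Power Analysis, reconcile the target to one fixed number per group and in total. State whether it counts participants randomised or participants evaluable, and how the 51 already enrolled relate to it. With the stated SDs, 10 per group gives about 81% power for 3 s and 20 per group about 99%. Describe the 130 as an enrolment ceiling only, and reconcile it with the 143 in the IRB form.
2. In Data Analysis, state that no comparison between arms is made before that number is reached. If a look at 20 on the way to 40 is wanted, specify it in advance. O'Brien-Fleming-type levels of about 0.0052 and 0.048 gave a simulated error rate of 5.05%, with 98.5% power for 3 s.
3. In item 1.19, limit the weekly meeting to conduct, safety and data quality, with outcomes pooled over groups. Send any by-arm outcome summary only to the existing Data Safety Monitoring Committee.

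The cost is a few sentences, with no extra participants, visits or staff. The change does not blind staff who already know the allocation. Whether those who test participants are blinded needs its own statement.

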1.20 What have you done to minimize any risks?

- Adverse event monitoring

1.25 Will any data from this project be stored for use in future research studies?

No

1.26 Does this project involve the collection or use of biological samples?

No

1.27 Are you requesting institutional certification to contribute human data or samples to a repository or database for broad sharing (public or restricted access)?

No

2. Participants

2.1 Will there be any adult participants?

Yes

2.1.a How many adult participants do you expect to consent or enroll under a waiver for this project?

143

2.1.b What is the age of the youngest adult participant?

18.0

2.1.c What is the age of the oldest adult participant?

No age limit

2.2 Will there be any minor participants?

No

2.3 Will there be any emancipated minor participants?
No

2.7 Do you plan to recruit/enroll non-English speaking people?
No

2.8 Do you propose to enroll any of the following in this study as participants?

- Employee of the PI or employee of a research team member
- Individual supervised by PI or supervised by member of research team
- Individual subordinate to the PI or subordinate to any member of the research team
- Student or trainee under the direction of the PI or under the direction of a member of the research team

No

2.9 Is this project about pregnant women?
No

2.10 Will this project involve fetuses?
No

2.11 Does this project involve the use of fetal tissue from any source?
No

2.12 Does this project recruit adult participants who may be incompetent or have limited decision-making capacity on initial enrollment into the study?
No

2.13 Does this project involve prisoners as participants?
No

3. Performance Sites

3.1 Indicate type of site(s) where research will occur (check all that apply):

- Academic Institution

3.2 Where will project procedures take place (check all that apply)?

- **School of Medicine**

3.3 Is this project also being conducted by other researchers at their own sites (e.g. a multi-site collaborative project)?
No

4. Drugs/Devices

4.1 Does this project involve:
Yes **No**

- Drug(s) (including radioisotopes)
- Use of contrast agent(s)
- Other substance injected, ingested, or applied to the body
- Testing a Device (Including companion devices, software, mobile health devices, assays, not FDA approved or outside approved indications, etc.)
- Combination product (as determined by the FDA - must have FDA documentation identifying this as a combination product)

4.2 Does this project involve a drug washout (asking participant to stop taking any drugs the participant is currently taking)?
No

4.3 Will any participants receive a placebo in place of standard therapy?
No

5. Privacy & Confidentiality

5.1 Indicate your plans to protect the privacy interests of the participants during the conduct of the study (check all that apply):

- Only the minimum necessary private information is collected for the purposes of the study
- Any procedures or interventions conducted as part of the study will be conducted in private setting to the extent possible
- Recruitment/consent will occur in a private setting
- Participants will be able to ask questions in a private setting

5.2 Are you collecting or using the Social Security Number of any participants for any purpose?
Yes

5.2.a Provide the intended usage of SSN:
• To provide compensation to participants

5.3 Project uses paper or hard copy consents, surveys, data collection forms, research subject binders, or other hard copy materials (check all that apply):
Yes

- All materials are stored in secured environment
- Access is limited to research team members only

5.4 Project collects, stores and/or transmits electronic data on mobile devices, desktop computers, servers including cloud servers, email, or any other information in electronic form (check all that apply):
Yes

- Data in Redcap
- Password protected
- Access is limited to research team only

5.5 Project collects or uses biologic specimens (check all that apply):
No

5.6 Identify any additional protections in place for data and or samples (check all that apply):
• No additional protections

Remote Limb Ischemic Conditioning to Enhance Performance and Learning

Study Objectives	
The objective of this research study is to determine if remote limb ischemic conditioning (RLIC) can serve as an agent to enhance motor learning. The immediate goal is to test the combination of RLIC with motor training in neurologically intact, middle-aged and older adults. The long term goal is to determine if RLIC, when compared to sham treatment, augments the learning that occurs during a rehabilitation training exercise in people who have motor deficits following stroke.

Background Rationale	
It is now understood that the nervous system has remarkable adaptive capacity. Specifically, the central nervous system retains its ability to reorganize in structure and function in response to behavioral experience in neurologically intact people and in individuals with neurological injury. Motor learning guides the adaptation of the central nervous system and is an essential component of effective training paradigms.
 
There is a growing body of literature which suggests that inducing a transient state of systemic ischemia has the potential to induce spinal plasticity, strengthen spared pathways to motoneurons, and lead to improved motor recovery following neurological injury.^{1,2} Specifically, daily systemic ischemic conditioning has been shown to improve both forelimb and respiratory motor function in rodent models of chronic cervical spinal injury.^{1,3} Moreover, systemic ischemic conditioning resulted in increased ankle strength (single session)² and augmented walking speed and endurance (5 sessions)⁴ in humans with motor incomplete spinal cord injuries.
 
In a related area of research, it has been shown that ischemic conditioning administered peripherally represents a strategy for harnessing the body's endogenous protective capabilities against lethal levels of ischemia. With this technique, applying brief ischemia and reperfusion to a remote organ or tissue results in significantly reduced damage from subsequent exposures to ischemia. For example, applying a tourniquet and creating ischemia in a rat's hindlimb for 10 minutes reduced the extent of cardiac abnormalities following a sustained ischemic insult.⁵ This same phenomenon has been shown in humans. Applying an inflated blood pressure cuff to the upper or lower limb has shown efficacy for protection in people undergoing cardiac surgeries,^{6,7} undergoing elective surgery to repair abdominal aortic aneurysm,⁸ experiencing MI,⁹ and with symptomatic intracranial arterial stenosis.⁷
 
The mechanisms underlying the neuroplastic and neuroprotective effects of ischemic conditioning are not fully understood. At this time, the literature indicates that there are both humoral and neural mechanisms responsible for the protection and the plasticity. It is clear that ischemic conditioning results in widespread physiological effects and that the observed effects work through multiple mechanistic pathways.
 
The next translational step is to investigate whether combining ischemic conditioning with behavioral training has the ability to augment motor learning. Specifically, we will employ remote limb ischemic conditioning (via inflation/deflation of a blood pressure cuff) with the objective of activating the endogenous pathways shown to elicit neuroplasticity. If eventually effective, RLIC could have profound effect on the rehabilitation and recovery of motor function in people with stroke. It is important to first start this translational investigation in neurologically intact people in order to determine optimal protocols for people with stroke.


	
The purpose of this study is to test if remote limb ischemic conditioning will enhance motor learning in neurologically intact middle-aged and older adults who are of a similar age and present with similar comorbidities as persons with stroke. . We previously found that combining behavioral training and RLIC facilitated motor learning in healthy young adults under 40.¹⁰The primary aim of this study is to determine if training + RLIC facilitates the learning of motor tasks in an older population beyond the healthy young population that we have previously tested.
																
Study Design	Between subjects repeated measures design. Please refer to Figure 1.																
Groups	
Group 1: Neurologically Intact Subjects + RLIC conditioning Group 2: Neurologically Intact Subjects + sham conditioning
 
Subjects who qualify and consent will be randomly assigned to either group 1 or 2.. Allocation will be concealed from those responsible for assessing subjects for eligibility and entry into the study (e.g. sequentially numbered, opaque, sealed envelopes).
																
Number of Subjects & Power Analysis	
Based off of our pilot data on the balance training task we need the following total sample sizes moving forward (see Table 1 below) to achieve at least 80% power to detect the mean differences of change scores (posttest – pretest) between the two treatment groups (RLIC vs. sham) based on a two-sample t-test at a significance level of 0.05. The standard deviations for change scores are assumed to be 2.5 seconds and 1.9 seconds for the RLIC and sham groups, respectively. Moving forward, we will recruit 10 subjects per group (n=40). This will give us the ability to detect differences on the balance task of at least 3 seconds or more. Differences less than 3 seconds (and smaller effect sizes) are unlikely to be clinically-relevant in future target populations. We continue to request permission to enroll 130 subjects total 51 of whom have already been enrolled) to allow for screen failures and participants who do not complete all study visits.
 
Table 1. Power analysis
 
  
 Mean difference of change score	Total sample size (assume equal sample size in each group)	
   
 7 seconds	12 (with actual power 93%)	
 
 6	12 (with actual power 85%)	
 
 5	15	
 
 4	21	
 
 3	30	
 
 2	63	
 
 1	237	
  
	Mean difference of change score	Total sample size (assume equal sample size in each group)	7 seconds	12 (with actual power 93%)	6	12 (with actual power 85%)	5	15	4	21	3	30	2	63	1	237
Mean difference of change score	Total sample size (assume equal sample size in each group)																
7 seconds	12 (with actual power 93%)																
6	12 (with actual power 85%)																
5	15																
4	21																
3	30																
2	63																
1	237																
Inclusion & Exclusion Criteria	
Inclusion Criteria
 
 1) At least 18 years old. 2) Cognitive skills sufficient to actively participate. 
Exclusion Criteria
 
 1) History of neurological condition, ADD, ADHD, balance impairment, or vestibular disorder. 2) History of sleep apnea. 3) History of lower extremity condition, injury, or surgery which could compromise performance on motor training task. 4) Any extremity soft tissue, orthopedic, or vascular injury which may contraindicate RLIC. 5) Any cognitive, sensory, or communication problem that would prevent completion of the study. 																

	
6) Current use of medication for, or treatment with: systemic inflammation, spasticity, selective serotonin reuptake inhibitors.
 
7) Current intensive weight lifting or interval training exercise.
 
8) Current substance abuse or dependence.
 
9) If participant lives further than one hour away and is unwilling to travel for assessment and treatment sessions.

Concomitant Medications/Training	Medications for the management for other co-morbid conditions not listed in the exclusion criteria are permitted. Regular, light exercise is permitted. See exclusion criteria for exercise that is not permitted.
Order of Experiment/ Study Visits	
This study involves 9 total visits. Participants will be in the study for up to 6 weeks.
 
The first 2 visits (D1 and D2) will take approximately 1.5 hours and 1 hour, respectively, and consist of RLIC/sham conditioning alone. The following 5 visits (D3-D7) will take approximately 2.0-2.5 hours and consist of RLIC/sham conditioning followed by motor training. The final two visits (F/U1 and F/U2) take place two and four weeks after D7 and will last approximately 30 minutes each. Please refer to Figure 1 for details about study visits.
 
D1: A trained clinical interviewer will provide informed consent and conduct a structured clinical interview. Eligible participants will be asked to complete descriptive measures. Next, researchers will assess pretest performance on the two outcome measures. After the pretest, subjects will undergo one set of RLIC or sham conditioning.
 
D2: Subjects will undergo one set of RLIC/sham conditioning.
 
D3-7: One set of RLIC or sham conditioning will be performed and then behavioral training will commence.
 
F/U1-2: Posttest performance will be assessed on the two outcome measures. Participants will not receive RLIC or sham conditioning during the follow-up visits. During the second follow-up session, participants will fill out a survey indicating whether they think that they received RLIC or sham treatment.

Conditioning Parameters	
Remote limb ischemic conditioning will be achieved via blood pressure cuff inflation to 20 mmHg above the subject's resting systolic blood pressure on the dominant upper extremity. Sham conditioning will be achieved via blood pressure cuff inflation to 10 mmHg under the subject's resting diastolic blood pressure, on the dominant upper extremity.
 
One set of RLIC or sham conditioning consists of 5 cycles of alternating 5 minutes of inflation, 5 minutes of deflation. One set of RLIC/sham conditioning will be performed per day on D1 and D2 and on D3-7. RLIC will always be performed before beginning behavioral training on D3-D7.
 
Subjects will be blinded to their group assignment (RLIC vs. sham).

Behavioral Training Parameters	
Participants will receive behavioral training on D3-D7 on a balance training task (15 minutes; rest breaks as needed)
 
The balance training task is a lower extremity standing balance task.¹¹ The balance task requires subjects to stand on a movable platform (stability platform, model 16030L, Lafayette Instrument) and to keep the platform in a balanced, horizontal position.¹¹ This is a lab-based test. This motor task was selected because it simulates the balance required for

	daily function, and can be easily modified to the appropriate level of difficulty in accordance with each subject's motor abilities.
Descriptive measures	Demographic information, including age, dominant side, gender, ethnicity, race, level of physical activity, first day of last menstrual cycle, height, body weight, employment status, education level, living status, co-morbidities, and current medications will be collected on all subjects during D1.
Primary Outcome Measures	
The outcome measure is change in balance score on the balance task.
 
Performance on the balance task will be quantified by identifying the number of seconds in a 30-second trial that an individual is able to maintain the platform within $\pm 3^\circ$ of horizontal. 5 trials are averaged for the baseline, after the intervention, and at follow-ups.
 
Balance change scores will be computed as the difference from the end of intervention minus the baseline (in seconds).

Data Analysis	
Data will be analyzed using a mixed model analyses examining group differences and interactions between group and various subject characteristics.
 
Our first hypothesis is that both the RLIC and sham groups will demonstrate improved performance on the balance task and arm task, with practice (main effect of time). Secondly, we hypothesize that RLIC will facilitate motor learning to a greater extent than the sham group, so that subjects given RLIC will demonstrate greater improvements in performance on the balance task and arm task than individuals given sham treatment (group x time interaction).
 
Additional analyses are planned per the funded project and include explorations into how various subject characteristics influence/interact with the RLIC vs. sham conditioning. These factors include age, sex, BMI, and the presence/absence of cardiovascular comorbidities and medications.

Safety Considerations & Monitoring	
The risks of participating in the rehabilitation intervention are minimal and are similar to the risks encountered during routine physical and occupational therapy services. The most likely risk during motor training tasks is fatigue. Fatigue will be monitored with the RPE scale during each session and rest breaks will be given as needed. There is also a small risk of falling during participation in the balance task portion of this study. Subjects will be permitted to use a handrail as needed for safety during the balance task and a trained research assistant will be immediately adjacent to the subject at all times.
 
In order to monitor for safety, we will continuously monitor for headaches, pain, lightheadedness, dizziness, altered vision, respiratory distress, cyanosis, and spasms. We will record and monitor heart rate, blood pressure, and oxygen saturation before, during, and after each set of RLIC. Sessions will be terminated if heart rate <40 bpm or >160 bpm, systolic BP <85 mm Hg or >160 mm Hg, or if O₂ saturation $<75\%$. Moreover, during the second follow up session, all subjects will be asked to fill out a questionnaire related to the presence of adverse effects that resulted from participation in this study.

Investigators	PI: [name] [name]
Number of Centers	1 center: Washington University School of Medicine
Key References	Please see the reference list.

[figure not shown]

Figure 1 Subjects will participate in 9 total sessions. D1 and D2 are conditioning alone. Remote limb ischemic conditioning (RLIC) involves 5 cycles of 5 minutes of upper extremity peripheral ischemia (induced either by a blood pressure cuff inflated to 20 mmHg > systolic BP), alternating with 5 minutes of no ischemia. For the next 5 consecutive days, subjects receive a combinational intervention of RLIC plus training. On training days, subjects undergo the RLIC and perform 15 minutes of standing balance training and 15 minutes of cognitive training. The final trials of the two training items will serve as posttest measures. Performance on standing balance and associative recognition tasks are measured at BL, at the beginning of training day 1, at the end of training days 1-5, and at each F/U.

